03	10/29/2021	Revised randomization method: covariate constrained randomization instead of matched pair	Allows balance on a greater number of cluster characteristics than matched pair, allows an odd number of clusters.
03	10/29/2021	Self-report data collection will use telephone surveys at all timepoints, not just baseline. There will be no web-based survey collection.	Changed to keep mode consistent, avoid potential mode differences
03	10/29/2021	Revised consent procedures: addition of signed e- or paper consent for participation in the trial	Signed consent required by our Institutional Review Board
04	07/01/2022	Change from cluster to individual randomization	Changes in health care delivery system now allow individual randomization. Individual randomization yields more assurance of comparable balance between study arms and higher likelihood of balanced sample size by arm
04	07/01/2022	Revised inclusion: expand age from >50 to >18	Expands sample to help meet enrollment targets
04	07/01/2022	Expanded recruitment pool to include individuals with type 2 diabetes with current prescription for insulin regardless of Karter risk stratification	Expands screening to help meet enrollment targets. No change to requirement for severe hypoglycemia in past 12 months or current impaired awareness of hypoglycemia.
04	07/01/2022	Update to Study Team: replacement [name] with [name]	Administrative change: [name] has left Kaiser Permanente Washington
05	11/29/2023	Addition of new secondary outcomes of glycemic control	New outcomes consistent with International Consensus on Use of Continuous Glucose Monitoring. Will be important to assess potential

		from Continuous Glucose Monitoring (CGM) data	intervention effects on frequency of high blood sugars and variability of blood glucose levels
05	11/29/2023	Revised plan for mediation analysis	Revised mediation analysis to reflect an updated approach using the causal mediation framework instead of the Baron and Kenney framework
05	11/29/2023	Revised analysis plan for handling missing data	Lowered the threshold for attrition that would trigger use of missing data methods to account for possible selection bias (from 15% to 10%). Other editorial changes to analysis plan were made for clarity, but were not substantive.
06	11/27/2024	Clarified clustering level for analysis	Revised analysis plan to account for patient clustering in the intervention arm within group training session cohorts rather than within clinic.

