- Baseline outreach and engagement in structured educational sessions: KPWA nurses specializing in diabetes will call participants and coordinate care for severe hypoglycemia risk factors as in the proactive care group. Nurses will elicit and address barriers for attending MyHC-TD2 training.⁴¹⁻⁴³ Participants will be mailed the MyHC-TD2 Glucose/Hypo diary and Participant Handbook in preparation for structured educational sessions. They will have the same nurse care manager throughout the intervention.

- Structured Educational Session
1: Two diabetes nurse educators trained on the MyHC-TD2 protocol will lead online virtual group sessions (**Figure 1**). The

[figure not shown]

Figure 1: MyHC-TD2 Education Activities

sessions will include 8 participants and will be conducted based on the Facilitator Guide and Participant Handbooks (**Appendix B**). Educational session #1 will be approximately 3 hours. Nurse educators will encourage participants to reflect on personal hypoglycemia events using the Glucose/Hypo diary. The

session will promote patient understanding and self-management strategies by group discussion of the MyHC-T2D compass points. Diaries will be completed over the first 4 weeks of the study. Daily 4-point and weekly 8-point blood glucose profiles will be done to determine times of increased hypoglycemia risk including at night and allow reflection on possible prevention strategies.

- ***Telephone Review:*** Approximately 2 weeks after the first educational session, nurse care managers will call participants for a 10- to 15-minute review. Nurses will discuss progress and review the Glucose/Hypo diary. They will encourage reflection on any hypoglycemia events and self-management strategies.
- ***Structured Educational Session 2:*** A diabetes nurse educator will lead an online virtual follow-up session with participants in their original groups. This 60-minute session, led by the same diabetes nurse educator as the first session, will facilitate discussion on progress with reference to the 4 points of hypo compass. Participants will be encouraged to reflect on hypoglycemia symptoms experienced during each event including subtle symptoms with review and discussion of the treatments implemented.

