Figure 3 shows the study flow diagram and **Figure 4** the schedule of enrollment, interventions and assessments. Participants in the proactive care management group will receive one standardized proactive outreach call from KPWA nursing staff, with follow up as indicated by the participant's needs. Participants in the proactive care management + MyHC-T2D group will receive the same standardized proactive outreach call in addition the standardized MyHC-T2D educational intervention, delivered over approximately three months. As described above, self-report data will be collected at baseline, 6-, 10- and 14 months, and CGM and EHR data at baseline and 14 months. Duration of participation for an individual participant will be 14 months from baseline data collection.

[figure not shown]

Figure 3: Study Flow

Figure 4. Schedule of enrollment, interventions, and assessments

TIMEPOINT	Allocation	STUDY PERIOD				
		Enrollment		Post-Enrollment		
		Pre-enrollment	Pre-enrollment	Baseline	6 month	10 months
ENROLLMENT:						
Identification		X				
Telephone screen			X			
Informed Consent			X			
Individual randomization			X			
INTERVENTIONS:						
Proactive care management				↔		
Proactive care management + MyHC-T2D				↔	↔	
ASSESSMENTS:						
Primary Outcome: Self-report severe hypoglycemia events			X	X	X	X
Secondary outcomes:						X
Self report measures			X	X	X	X
CGM Measures			X			X
EHR measures			X			X
Process Measures						X
Qualitative Assessments		X	X	X	X	X

2f. Sample size

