We estimate 256 patients (128 randomized to proactive care management, and 128 randomized to MyHC-T2D) will consent and complete the baseline survey. To account for loss to follow-up, we assume an 80% response rate for the primary outcome measured at 14-months, for an analytic sample size of 204 (102 per group). Power calculations for comparing two independent proportions and assumed a 0.05 type I error rate. Assuming 60% of patients in the proactive care management group will self-report having had a severe hypoglycemia event in 12-month look back (yes/no), we have 90% power to detect a 22.6% absolute difference between groups (i.e. 37.4% severe hypoglycemia rate in MyHC-T2D arm) for the primary outcome. We have 80% power to detect an absolute difference of 19.7% between groups. Our study has power to detect a meaningful difference (30% or more reduction in frequency of self-reported severe hypoglycemia events).⁵⁴ Other studies including for the original *my hypo compass* have similar or larger effects on severe hypoglycemia reductions.²⁵⁻²⁹ We also have 80% power to detect a 1.4% difference and 90% power to detect a 1.6% difference between groups in the secondary outcome of the percent time with biochemical hypoglycemia (<54 mg/dL); this difference is consistent with the effect seen with the original *my hypo compass*.^{25,32}

2g. Recruitment

We will recruit the study population in two steps.

Step 1, Automated risk stratification: We will identify a cohort of adults (≥ 18 years) with T2D receiving primary care at KPWA. We will identify all individuals with either a current prescription for insulin or who have intermediate-to-high risk for a SH event based on our hypoglycemia risk-stratification tool.

Step 2, Phone screening for verbal consent and to identify patients at highest SH risk: We will mail eligible participants an invitation with study brochure and notification that staff will call them about the study. KPHRI Survey Research Program (SRP) members will then call the potential participant to explain the study, assess eligibility and interest, and conduct informed verbal consent with those who are eligible and interested. We expect 1001 eligible. Based on a similar recruitment⁵⁵ and participation in other diabetes education trials, we anticipate at least 25% will consent and complete baseline data collection.⁵⁶

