Participation in this study is voluntary. Even after consent, participants may choose to not do specific study components such as CGM data collection. They may decline survey questions or choose not to participate in intervention activities. Participants will not be considered withdrawn from the study unless they state clearly that they wish to withdraw. For participants who do not complete specific activities but do not withdraw consent, we will continue to use what information they have provided and will extract and use EHR data as described in the consent process. If participants withdraw their consent, we may still use information collected before withdrawal, but will not collect any additional information and will destroy any record of their name or other information that may identify them. This will be clearly stated in the consent materials and reviewed as part of the informed consent process.

4a.6. Process evaluation

In addition to collection of data for primary and secondary outcomes described above, we will conduct a process evaluation to assess whether the interventions were implemented as planned and to test and refine the hypothesized causal pathways (Figure 5). These results will be essential to ensure future implementations of severe hypoglycemia prevention are centered on patient needs and are feasible and acceptable for healthcare providers and systems.

We will use qualitative and quantitative methods for assessing the *fidelity, dose and mechanism* of the intervention.

Qualitative assessments: To assess delivery *fidelity* and *dose* to clusters and individuals, we will observe nurse care managers and diabetes nurse educators working with participants and interview them after interventions.⁵⁷ For observations of nurse care managers, we will develop a tool to capture information on protocol integrity for outreach calls to patients in both comparator groups. We will do observations in the last 2 months of intervention implementation to separate evaluation from earlier fidelity monitoring and feedback training to nurses conducted by the intervention team. We will observe nurses on initial proactive care management outreach calls in each comparator group. We will observe nurses on the two follow-up educational calls in the MyHC-T2D group. We will also observe selected MyHC-T2D group educational sessions facilitated by the diabetes nurse educators.

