- **EHR data** will be extracted by the study programmer from automated administrative and EHR data sources, including the KPHRI Data Warehouse, a research-centric repository of datasets maintained by the Research Institute. Data are stored in Teradata, SQL Server, and SAS format and cover enrollment, demographics, diagnoses and procedures, vital signs, pharmacy, lab tests, costs. A rich collection of powerful SAS macros can be used in conjunction with the KPHRI data. KPHRI data warehouse content and usage are documented by a wiki-based system authored by the data warehouse's architects, managers, and users. Access and security for electronic data sources are described below in Section 3. Ethics and Dissemination, Confidentiality.

4c. Statistical methods

Comparative effectiveness analyses will apply intent-to-treat principles, with study participants analyzed based on randomization group, regardless of intervention received. To assess comparability across study groups, we will summarize demographic characteristics and responses to baseline surveys in the two comparison groups. The preliminary analysis plan defines the primary outcome as a binary indicator for whether or not (yes/no) the participant self-reported having had a severe hypoglycemia event in the prior 12-months, assessed 14 months after baseline. We will estimate relative risk of severe hypoglycemia in the MyHC-T2D group vs. proactive care management group by fitting a modified Poisson regression model with the binary self-report measure as the dependent variable and randomization group as the independent variable. Models will adjust for age, sex, risk score, and the number of self-reported severe hypoglycemic events in the 12 months prior to baseline. Models will be fit using generalized estimating equations (GEE) and robust variance estimation to account for correlation due to patient clustering in the intervention arm within group training session cohorts, and the misspecified mean-variance relationship in using Poisson regression for a binary outcome.

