Process Evaluation: We will use descriptive analysis to assess intervention recruitment, reach and delivery. If significant differences ($p<0.05$) between intervention groups are found for the primary outcome, we will perform mediation analysis to test the hypothesis that the possible causal pathway for reducing the occurrence of severe hypoglycemia is through improvements in hypoglycemia knowledge, hypoglycemia awareness, self-efficacy of hypoglycemia management, blood glucose testing, and hypoglycemic medication adjustment and other factors in causal pathway in **Figure 2**. Mediation analysis will use a regression-based approach within the causal mediation framework,⁵³ separating the total intervention effect into a natural indirect effect (effect occurring through the mediator), and a natural direct effect (effect through all other pathways). To estimate these effects, we will use either a log-linear or Poisson model for the outcome model (depending on whether the primary outcome is defined as a binary or count variable), and linear regression for the mediator model. The effect of each mediator will be estimated in separate models.

4d. Trial monitoring

4d.1 Data monitoring

This study will have a Data Safety Monitoring Board (DSMB) to ensure safety of research participants. The DSMB will include an external researcher with prior DSMB experience (the chair), and two clinicians with expertise in type 2 diabetes and in the treatment and care for patients with severe hypoglycemia and impaired hypoglycemia awareness. The DSMB will meet once in the first 6 months after study funding and prior to patient enrollment to review study protocols and plans for study reports (enrollment, completion, and adverse event-reporting tables by study group) and recommend changes. The study team will track participant-reported serious adverse events whether related or not to study participation. The team will provide ongoing reports to the DSMB and the Institutional Review Board. The DSMB will meet twice per year, in person or by phone, as directed by the committee. The study Principal Investigator, biostatisticians, and project manager will attend all open portions of DSMB meetings.

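### Section 4c names no small-sample correction for a GEE sandwich variance resting on about 16 session groups; used plainly with z, it would reject about 5.5% to 6.2% instead of 5%

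*Combined protocol and SAP*

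**What the plan says.** Section 4c estimates the relative risk by modified Poisson regression, adjusted for age, sex, risk score and the number of severe events before baseline. The models will be "fit using generalized estimating equations (GEE) and robust variance estimation to account for correlation due to patient clustering in the intervention arm", the clusters being the group training session cohorts. The version 06 entry in the Protocol Amendment History shows that this was deliberate: "Revised analysis plan to account for patient clustering in the intervention arm within group training session cohorts rather than within clinic". Later in 4c, GEE with robust sandwich errors is also adopted for the secondary outcomes.

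The number of clusters has to be derived. Section 2c.2 says that the "sessions will include 8 participants and will be conducted based on the Facilitator Guide and Participant Handbooks", and section 2f plans "128 randomized to proactive care management, and 128 randomized to MyHC-T2D".

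No section names a small-sample correction, a reference distribution, degrees of freedom or a working correlation.

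Two smaller points are left implicit. Section 4a.5 says of participants, "They may decline survey questions or choose not to participate in intervention activities", and 4c keeps "study participants analyzed based on randomization group, regardless of intervention received", so a MyHC-T2D participant who is never placed in a session has no stated cluster. The paragraph on outcomes measured at 6, 10 and 14 months does not restate the cluster.

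**The concern.** The sandwich variance is built from squared cluster totals of residuals. With few clusters, or several fitted coefficients, those residuals are too small on average and the standard error is biased downwards. The total number of clusters looks comfortable here, at about 16 + 102 = 118, but the MyHC-T2D arm contributes only about 16 of them.

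The text leaves open how this is handled. One analyst could take the plain sandwich with z and another t on 15 degrees of freedom, so the critical value would move from 1.96 to 2.13. A primary result near the threshold could fall on either side of it. The same p-value decides a later step: if significant differences "between intervention groups are found for the primary outcome, we will perform mediation analysis". The choice should therefore be in writing before the 14-month outcomes are analysed.

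**Working it through.** **Inputs from the plan.** 128 per arm, 80% response, 102 analysed per arm, 60% control rate, type I error 0.05 (all section 2f); groups of 8 (section 2c.2); model and covariates (section 4c).

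**Assumed, because the documents give no value.** ICC of 0, 0.02, 0.05 and 0.10; two-sided test; independence working correlation; response missing at random with complete-case analysis.

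**Step 1: the plan's own power.** Two proportions, pooled variance under the null, n = 102 per arm.

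- 60% vs 37.4%: SE0 = sqrt(2 × 0.487 × 0.513 / 102) = 0.0700; SE1 = sqrt((0.6 × 0.4 + 0.374 × 0.626) / 102) = 0.0682; (0.226 − 1.96 × 0.0700) / 0.0682 = 1.30, so power is 90.4%.
- 60% vs 40.3%: (0.197 − 1.96 × 0.0700) / 0.0686 = 0.87, so power is 80.8%.

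The stated 90% and 80% are reproduced.

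**Step 2: clusters.** 128 / 8 = 16 session groups. After 80% response, about 102 / 16 = 6.4 analysed per group, plus about 102 singleton controls.

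**Step 3: size under the null.** Simulation with 60% in both arms, a beta-binomial group effect in the MyHC-T2D arm only, log-link Poisson estimating equations and four covariates. There were 20,000 trials per ICC (Monte Carlo SE about 0.16 points).

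| Variance and reference | Mean SE / true SD | Rejection at ICC 0, 0.02, 0.05, 0.10 |
|---|---|---|
| Plain, z | 0.962 to 0.966 | 5.8%, 5.9%, 5.7%, 6.1% |
| Plain, t on 15 df | same | 3.8%, 4.0%, 4.0%, 4.2% |
| Kauermann-Carroll, z | 0.990 to 0.996 | 5.0%, 5.3%, 5.1%, 5.4% |
| Mancl-DeRouen, z | 1.020 to 1.029 | 4.4%, 4.7%, 4.5%, 4.7% |

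A hand check from the SE ratio agrees. Plain with z has an effective critical value of 1.96 × 0.965 = 1.891, a two-sided normal tail of 5.9%. With t it is 2.131 × 0.965 = 2.056, a tail of 4.0%. Kauermann-Carroll gives 1.96 × 0.993 = 1.946, a tail of 5.2%.

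**Step 4: sensitivity, plain sandwich with z.**

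- Four prognostic covariates, 8,000 trials per cell: 5.7% to 6.2% (Kauermann-Carroll 4.9% to 5.6%).
- No covariates, 200,000 trials per cell: 5.5% to 5.7% with 16 groups, 5.7% to 6.0% with 13, and 5.3% to 5.4% with 20.

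**Step 5: how much comes from the groups.** At ICC 0 with the groups ignored, the SE ratio is already 0.982. Of the 3.5% shortfall at ICC 0 (ratio 0.965), 1.8 points are therefore there without the groups. Nor does the shortfall clearly grow with the ICC.

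**Step 6: power for 60% vs 37.4%**, 10,000 trials per cell.

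| ICC | Plain | Kauermann-Carroll | Loss (points) |
|---|---|---|---|
| 0 | 90.0% | 88.8% | 1.2 |
| 0.05 | 84.8% | 83.0% | 1.8 |
| 0.10 | 80.9% | 78.7% | 2.2 |

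The fall down each column is the effect of clustering itself. Only the last column is the price of the correction.

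**The case against.** The strongest case against is that this hardly matters. The excess is about 0.5 to 1.2 points of type I error, and it arises only if the analyst pairs the plain sandwich with z. The documents name no analysis software and no default. With t on 15 degrees of freedom the test errs the other way. That stands. A reader might infer that the plan has an inflated error rate built in; it does not, because the direction is left open.

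Two further inferences are tempting.

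- **Missing cluster for non-attenders.** A reader might infer that this distorts the test. Without covariates, with 10 to 13 groups and 10 to 30 analysed non-attenders, rejection was 5.2% to 6.3% when they were singletons and 5.5% to 6.3% when pooled as one cluster. Those ranges largely overlap, and no consequence for the error rate has been shown. Since clustering is defined by session cohort, a participant without a cohort most naturally counts as a singleton, as controls do.
- **Repeated self-report models.** A reader might infer serious inflation, because clustering on participant gave 7.9% at ICC 0.05 and 9.7% at 0.10 for a continuous outcome with assumed within-person correlation 0.5. That requires the analyst to depart from the plan's evident intent: 4c says GEE is also used for secondary outcomes, and the version 06 entry sets session cohorts for the analysis plan generally. At ICC 0 to 0.02 participant clustering did no worse than session clustering. The question does not arise for CGM and EHR outcomes: "self-report data will be collected at baseline, 6-, 10- and 14 months, and CGM and EHR data at baseline and 14 months".

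A fair technical objection remains. Section 4c says that if attrition exceeds 10%, statistical methods will account for selection bias, and multiple imputation or weighting will be considered. The plan's own 80% response means 20% attrition, which crosses that line. The simulations analysed complete cases, so the percentages may not carry over exactly, and the fix has to cover those analyses.

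**Conclusion.** The point holds as a modest gap in pre-specification with a cheap remedy. If the plain sandwich is used with z, the standard error is about 3% to 4% too small and the nominal 5% test rejects about 5.5% to 6.2%; with t on 15 degrees of freedom it rejects about 4%. It matters only for a result close to the threshold.

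The figures rest on about 16 session groups (derived), an assumed ICC of 0 to 0.10, an independence working correlation and complete cases missing at random. The session clustering itself is worth keeping: at ICC 0.05 to 0.10, ignoring it rejected about 6.2% to 8.4%. The cluster for participants never placed in a session, and for the repeated self-report models, needs clarification only.

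**What to change.** Add to section 4c, before the 14-month outcomes are analysed:

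- All GEE models use a bias-corrected sandwich variance, for example Kauermann-Carroll with a z reference. If imputation or weighting is used, the same corrected variance is used within each imputed or weighted analysis.
- As clarification: the cluster is the session cohort for MyHC-T2D participants placed in one, and the individual for controls and for MyHC-T2D participants never placed in one. The same clusters apply in the 6-, 10- and 14-month models.

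The estimator should be named rather than left as a generic adjustment. A simple factor on the total cluster count would raise the standard error by only sqrt(118/117) = 1.004, or 0.4%.

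Mancl-DeRouen with z is an acceptable, slightly conservative alternative. The plain sandwich with t on 15 degrees of freedom is defensible but noticeably conservative.

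**Cost.** A few sentences and a standard software option, with no new data. With Kauermann-Carroll, intervals widen by about 3% and power at the 22.6-point difference falls by 1.2 to 2.2 points. With Mancl-DeRouen the figures are about 6% and 2.5 to 4.9 points. Part of that power loss is simply the excess rejection being removed. The correction is not perfect: for the repeated self-report outcome, session clustering with Kauermann-Carroll still rejected 5.4% to 6.0%, against 6.0% to 6.6% uncorrected.

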To retain participants and minimize data loss, we will provide \$100 incentive for completing data collection at baseline and 14 months (\$30 for the survey and \$70 for CGM at each time point) and \$30 for self-report-only measures at 6 and 10 months. Participants who agree to have an HbA1c test for the study at months will receive an additional \$25.

3. Methods: Assignment of interventions

3a. Allocation

After identifying potentially eligible patients based on EHR data, and verify eligibility, documenting verbal consent, collecting baseline data by phone, and receiving written consent, we will randomize study participants to one of our two intervention arms using a 1:1 allocation ratio. Randomization will occur by selecting sequential assignments from randomization sequences generated by the study biostatistician, and stored on a computer inaccessible to study staff. The randomization list will use permuted blocks of randomized size 4 or 8.

Randomization will be stratified by age (18-74 versus 75+ years) and risk score for severe hypoglycemia (moderate versus high risk), to ensure balance of these important risk factors of SH events across intervention arms. Individuals with low risk but using insulin will be randomized in the moderate risk strata. Randomization assignment will be concealed from the study staff verifying eligibility and will only be revealed after baseline data has been collected, and the next sequential randomization assignment has been requested. Outcomes will be measured and analyzed at the participant level.

3b. Blinding (masking)

Blinding or masking will be maintained for research staff collecting outcomes, including those collecting self-report and CGM data. However, participants, nurses, and providers engaged in the interventions cannot reasonably be masked to the study groups, nor can study staff conducting fidelity monitoring or those collecting qualitative data.

The study programmer and biostatisticians will have access to unblinded data to conduct data summaries by intervention group as necessary for reporting to the Data and Safety Monitoring Board (DSMB). The Principal Investigator and other study investigators will remain blinded until all study data for the relevant analyses is collected.

4. Methods: Data collection, management, and analysis

4a. Data collection methods

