Prior to conducting analysis of 14-month outcomes, we will look at the baseline distribution of the self-reported number of severe hypoglycemic events in the prior 12-months collected at baseline. If more than 60% of enrolled patients report 2 or more events, we will revise the primary outcome to be defined as the self-reported *number* of severe hypoglycemic events in the past 12-months, measured at 14-months post baseline (a count rather than a binary outcome and fit a Poisson regression model to estimate the rate ratio for severe hypoglycemia events for the MyHC-T2D group relative to the care management group. We will assess model fit, and consider zero-inflated models as an alternative, if the number of participants reporting zero events violates distributional assumptions of the Poisson model. If primary analyses use the binary outcome measure (i.e. fewer than 60% of patients report 2 or more events in the 12-months prior to baseline), but 40% or more of respondents report 2 or more events at 14-months, we will do a secondary analysis with the count variable as the outcome.

Generalized linear regression models estimated with GEE and robust sandwich errors will also be used to estimate intervention effects on secondary outcomes, with link function and error distribution appropriate for each outcome. For secondary outcomes measured at multiple follow-up time points (6-, 10- and 14-months post-baseline), we will fit a single regression model that includes outcome measures from all follow-up time points. Models will include indicator variables for time, intervention group, and interaction terms between these variables, to estimate intervention effects at each time point. Models will adjust for age, sex, risk score and the baseline measure of the outcome. For hypoglycemia-related health care utilization (urgent care and emergency department visits, hospital admits), we will follow a similar analytic plan as the primary outcome, including the process to determine whether to model these outcomes as binary or count variables.

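### If severe events are analysed as a count, the option to move to a zero-inflated model on the 14-month zeros replaces the stated rate ratio with a different quantity, and it is not needed

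*Combined protocol and SAP*

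**What the plan says.** The planned primary outcome is binary: any self-reported severe episode in the previous 12 months, asked at 14 months (section 2d.1). A count can enter by three routes, all in section 4c:

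- It becomes the primary outcome if more than 60% of enrolled patients report two or more events at baseline.
- It becomes a secondary analysis if the primary stays binary but at least 40% of respondents report two or more events at 14 months.
- Hypoglycemia-related utilization is to be handled in a similar way to the primary outcome, including the choice between binary and count.

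For the count, the plan will "fit a Poisson regression model to estimate the rate ratio for severe hypoglycemia events for the MyHC-T2D group relative to the care management group". The next sentence provides for a check of model fit and says the team will "consider zero-inflated models as an alternative, if the number of participants reporting zero events violates distributional assumptions of the Poisson model".

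GEE with robust variance is stated for the binary primary model and, later in the same section, for the generalized linear models of secondary outcomes. It is not restated for the count primary or for a zero-inflated model. For a count primary, the mediation paragraph of section 4c specifies a Poisson outcome model and no zero-inflated counterpart.

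**The concern.** The move from binary to count as primary is decided on baseline data, so it cannot be influenced by the result. The move from Poisson to zero-inflated is decided on the 14-month outcome itself. It is discretionary, and under section 3b the biostatisticians may see data by arm.

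The two models also do not answer the same question. Poisson regression compares mean event rates between the arms as randomized. A zero-inflated model has a zero part and a count part, and its count ratio applies to a latent group of people who can have events. The plan does not say which part would be the treatment effect or how the two would be combined into the rate ratio. An effect on whether people have any event is what the planned binary primary looks for, and it is the effect that the count part leaves out. A contingent primary analysis could therefore report an effect that was chosen after the outcome was seen and that is not the stated one.

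**Working it through.** **Inputs.** Section 2f: 102 analysed per arm, type I error 0.05 (taken as two-sided), 60% of the comparator arm with an event, and detectable differences of 22.6 and 19.7 points. Section 3a: 1:1 allocation. The documents give no mean, dispersion or proportion of zeros for the count, so every count distribution below is an assumption.

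**Step 1: the plan's own figure.** The plan states that "we have 90% power to detect a 22.6% absolute difference between groups". For two proportions, power = Φ[(d − 1.96·SE₀)/SE₁], with SE₀ from the pooled proportion and SE₁ from the separate proportions.

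- 60% vs 37.4%: SE₀ = √(2 × 0.487 × 0.513/102) = 0.0700; SE₁ = √((0.240 + 0.2341)/102) = 0.0682; (0.226 − 0.1372)/0.0682 = 1.30; power 0.904.
- 60% vs 40.3%: the same formula gives 0.808.

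The stated 90% and 80% are reproduced. They concern the binary outcome. The documents give no operating characteristic for a count analysis.

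**Step 2: does the switch change the quantity?** In a zero-inflated Poisson model, let s be the share of an arm that can have events and λ the mean count among them. The arm mean is sλ, so

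arm-level rate ratio = (s₁/s₀) × (λ₁/λ₀).

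The count coefficient estimates only λ₁/λ₀. Suppose the intervention acts only on the share, so λ₁ = λ₀. The proportion with any event is s(1 − e^−λ), so the ratio of those proportions also equals s₁/s₀, and the figures in section 2f can be used directly:

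- arm-level rate ratio = 0.374/0.60 = 0.62;
- zero-inflated count ratio = 1.00.

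This step needs no assumption about dispersion.

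**Step 3: is the switch needed?** Without covariates, log-link Poisson returns the ratio of the two arm means exactly. With covariates, consistency rests on the model for the mean, not on the Poisson shape. Extra zeros make the Poisson variance wrong, and a sandwich estimator deals with that.

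**Step 4: type I error.** Null simulations used 102 per arm and nominal 5%. The plan names no test for excess zeros, so a score test at p < 0.05 was assumed.

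*Set A* (3,000 runs in each of 11 scenarios, with no covariates). The rule was robust Poisson unless the score test was significant, then the zero-inflated Poisson count ratio.

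| Assumed counts | Switching rule, model-based zero-inflated errors |
|---|---|
| Poisson | 5.5% |
| True zero-inflated Poisson | 4.8% |
| Negative binomial, 25% zeros, shape 2 to 0.5 | 13.7% to 58.7% |
| Negative binomial, 40% zeros, shape 2 / 1 / 0.5 | 9.9% / 17.3% / 35.1% |
| Negative binomial, 60% zeros, shape 2 to 0.5 | 6.2% to 17.5% |

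Other results from set A:

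- Same rule with sandwich errors on the count part: 5.2% to 6.4%.
- Either zero-inflated coefficient may be claimed: 5.6% to 10.8%.
- Free choice among robust Poisson and the two zero-inflated parts: 9.3% to 13.4%.
- Poisson with sandwich variance and no switch: 4.9% to 5.9%.
- Poisson with model-based variance, 40% zeros, shape 1 and 0.5: 21.2% and 41.8%.

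*Set B* (negative binomial, mean 2 or 3, shape 0.5 or 1.0).

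| Analysis | Rejection under the null |
|---|---|
| Zero-inflated Poisson count part, model-based errors | 20-37% |
| Zero-inflated Poisson count part, sandwich errors | 5-8% |
| Either zero-inflated coefficient may be claimed | 9-12% |
| Plain Poisson, model-based errors | 27-46% |

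A separate run of the set B scenarios (400 trials each) gave 4-7% for zero-inflated negative binomial with model-based errors.

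**Step 5: limits.** A smaller simulation adjusted for the baseline count had about 360-400 usable runs per setting, some failed zero-inflated fits, and Monte Carlo error of about 2 to 5 points. In one setting (shape 2), robust zero-inflated Poisson gave 12.4% and Poisson GEE 8.5%. Robust variance therefore does not guarantee exact control at this sample size.

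For set B, the probability of two or more events is 1 − P₀ − P₁, with P₀ = (k/(k+μ))^k and P₁ = k·(μ/(k+μ))·P₀, where μ is the mean and k the shape. This gives 37% (μ=2, k=0.5), 44% (μ=2, k=1), 46% (μ=3, k=0.5) and 56% (μ=3, k=1). None exceeds 60%, and one is below 40%. The 60% trigger applies to baseline and these are 14-month counts, so they are not excluded, but nothing in the documents ties them to this trial.

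**The case against.** The strongest reply is that the plan is robust throughout. It uses GEE with sandwich errors for the binary primary and extends them to secondary outcomes, and a fair reader would carry them over to any count model. Treated alike, the zero-inflated count part is near nominal; treated alike with model-based errors, plain Poisson does worse than zero-inflated Poisson. The plan speaks of zero-inflated models in general, and the negative binomial version held its level. It only undertakes to consider them after checking fit. The binary outcome is the planned primary, and section 2b admits people with impaired awareness and no recent severe event, so the 60% trigger may be hard to reach.

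Most of this stands. A reader might infer that looking at the zeros in itself multiplies the type I error, or that the switch would happen routinely. The documents support neither. The large inflation comes from model-based errors with overdispersed counts, and a smaller part from the free choice of coefficient. How often a check would fire depends on a distribution and a test that the plan does not give.

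The reply does not meet the change of quantity. Sandwich errors do not turn a latent-class count ratio into an arm-level rate ratio. A zero-inflated mixture is also not a generalized linear model, so the stated GEE method and its clustering by training session do not carry over to it automatically.

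**Conclusion.** The concern holds for the quantity estimated and, conditionally, for the error rate.

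- **Quantity.** The switch can replace a rate ratio of 0.62 with a count ratio of 1.00 when the effect lies wholly in the share of people with events. This follows from the model's structure and the plan's own 60% and 37.4%.
- **Error rate.** About 20-37% (4 to 7 times nominal) in the assumed negative binomial scenarios of set B, but only with overdispersion and a zero-inflated Poisson model with model-based errors. It is about 5-8% with sandwich errors on the count part, and about 9-12% if either coefficient may be claimed. All of these rest on assumed distributions.
- **Reach.** A contingent primary, a triggered secondary and, by reference, utilization. The planned binary primary analysis is untouched.

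The point goes beyond missing detail, because a better method is already at hand: the Poisson model that the plan names, with the robust variance that it uses elsewhere.

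**What to change.** In section 4c:

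1. Make log-link Poisson GEE with robust variance, clustered by training-session cohort as in the primary model, the sole main analysis of any severe-event or utilization count, and report the arm-level rate ratio.
2. State the robust variance explicitly for the count model. Poisson with model-based errors would inflate the type I error at least as much as the zero-inflated Poisson model.
3. Keep any zero-inflated or negative binomial model only as a labelled sensitivity analysis, naming the coefficient to be reported and its variance estimator. The option need not be deleted.

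The cost is wording only, with no change to data collection or sample size. The statistical downside is possibly slightly lower efficiency than a correctly specified parametric model. The change should be dated before the 14-month counts are analysed; if they have already been seen, the report should say so.
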